11.7 Confidentiality of study documents and patient records

The investigator must ensure anonymity of the patients. Patients must not be identified by name in any documents submitted to Novartis. Signed ICFs and patient enrollment log must be kept strictly confidential to enable patient identification at the site.

11.8 Audits and inspections

Source data/documents must be available to inspections by Novartis or designee or Health Authorities.

11.9 Financial disclosures

Financial disclosures should be provided by study personnel who are directly involved in the treatment or evaluation of patients at the site prior to study start.

12 **Protocol adherence**

Investigators ascertain they will apply due diligence to avoid protocol deviations. Under no circumstances should the investigator contact Novartis or its agents monitoring the study to request approval of a protocol deviation, as no authorized deviations are permitted. If the investigator feels a protocol deviation would improve the conduct of the study this must be considered a protocol amendment. Unless such an amendment is agreed upon by Novartis and approved by the IRB/IEC/REB, it cannot be implemented. All significant protocol deviations will be recorded and reported in the CSR.

14.1 Dosing tables (Deferasirox FCT)

For each patient the investigator and/or pharmacist will calculate a target daily dose taking into account patient's body weight. When the calculated dose cannot be reached with the deferasirox FCT strengths available, the closest daily dose available will be prescribed.

The following dosing table provides an efficient combination of tablet strengths reaching a certain daily dose for each body weight range.

These dosing tables have been constructed for each dosing group using lower and upper body weight limits of 35 and 140 kg, respectively. This is taking into account that the study will enroll male or female adults.

Table 14-1	Dosing table for 3.5 mg/kg/day of Deferasirox FCT
------------	---

Pt Weight in Kg	Closest Dose	90 mg	180 mg	360 mg
35 - 38	90 mg	1	-	-
39 - 64	180 mg	-	1	-
65 - 90	270 mg	1	1	-
91 - 115	360 mg	-	-	1
116 - 140	450 mg	1	-	1

Pt Weight in Kg	Closest Dose	90 mg	180 mg	360 mg
35 - 45	270 mg	1	1	-
46 - 57	360 mg	-	-	1
58 - 70	450 mg	1	-	1
71 - 83	540 mg	-	1	1
84 - 96	630 mg	1	1	1
97 - 109	720 mg	-	-	2
110 - 122	810 mg	1	-	2
123 - 135	900 mg	-	1	2
136 - 140	990 mg	1	1	2

Table 14-2	Dosing table for 7 mg/kg/day of Deferasirox	FCT
	bosing table for a mg/kg/day of belefasitor	

	0	007		
Pt Weight in Kg	Closest Dose	90 mg	180 mg	360 mg
35 - 38	360 mg	-	-	1
39 - 47	450 mg	1	-	1
48 - 55	540 mg	-	1	1
56 - 64	630 mg	1	1	1
65 - 72	720 mg	-	-	2
73 - 81	810 mg	1	-	2
82 - 90	900 mg	-	1	2
91 - 98	990 mg	1	1	2
99 - 107	1080 mg	-	-	3
108 - 115	1170 mg	1	-	3
116 - 124	1260 mg	-	1	3
125 - 132	1350 mg	1	1	3
133 - 140	1440 mg	-	-	4

Table 14-3	Dosing table f	or 10.5 mg/kg/day	of Deferasirox FCT
------------	----------------	-------------------	--------------------

Table 14-4		-4	14	е	bl	Та	
------------	--	----	----	---	----	----	--

Novartis

Amended Protocol Version 01 (Clean)

Dosing table for 14 mg/kg/day of Deferasirox FCT

Pt Weight in Kg	Closest Dose	90 mg	180 mg	360 mg
35	450 mg	1	-	1
36 - 41	540 mg	-	1	1
42 - 48	630 mg	1	1	1
49 - 54	720 mg	-	-	2
55 - 61	810 mg	1	-	2
62 - 67	900 mg	-	1	2
68 - 73	990 mg	1	1	2
74 - 80	1080 mg	-	-	3
81 - 86	1170 mg	1	-	3
87 - 93	1260 mg	-	1	3
94 - 99	1350 mg	1	1	3
100 - 106	1440 mg	-	-	4
107 - 112	1530 mg	1	-	4
113 - 118	1620 mg	-	1	4
119 - 125	1710 mg	1	1	4
126 - 131	1800 mg	-	-	5
132 - 138	1890 mg	1	-	5
139 - 140	1980 mg	-	1	5

14.2 Examples of light meal

Example 1:	amount	kcal	g total fats
Wheat Bread or Toast	2 slices	138	2
jams, preserves, all flavors	1 Tablespoon	109	0
banana	medium (7-7 7/8" long)	105	0
orange juice	1 cup	114	0
skim milk	1 cup	83	0
	Total:	549	2

Example 2:	amount	kcal	g total fats
Pita Bread	1 medium (5.25" across) pita	124	1
	1 Tablespoon hummus or 2 oz.		
hummus or deli chicken/turkey	meat	27	1
apple	medium (2.75" across)	72	0
salsa, red, cooked	6 Tablespoons	26	0
	4 carrot sticks (3" long) and small		
carrots & celery sticks	5" stalk of celery	14	0
	Total:	263-295	2

Example 3:	amount	kcal	g total fats
yogurt, fruit, low-fat	6 oz.	173	2
banana	medium (7-7 7/8" long)	105	0
orange juice	1 cup	114	0
skim milk	1 cup	83	0
	Total:	475	2

Example 4:	amount	kcal	g total fats
vegetable chicken noodle soup, canned	1 cup	70	2
baked potato, peel not eaten	1 medium (2.25-3" across)	121	0
skim milk	1 cup	83	0
banana	medium (7-7 7/8" long)	105	0
	Total:	379	2

Novartis	Confidential		Page 79
Amended Protocol Version 01 (Clean)		Protocol No. CICL670F2203	
Example 5:	amount	kcal	g total fats
egg whites, cooked, no fat added	2 large egg whites	32	0
salsa, red, cooked	6 Tablespoons	26	0
Wheat Bread or Toast	2 slices	138	2
jams, preserves, all flavors	1 Tablespoon	109	0
orange juice	1 cup	114	0
skim milk	1 cup	83	0
	Total:	502	2
Example 6:	amount	kcal	g total fats
chicken, boneless, skinless			U
baked	0.5 cup diced	111	2
salsa, red, cooked	6 Tablespoons	26	0
white rice, cooked, no fat added	0.5 cup	102	0
black beans, canned or cooked			
from dry, no fat added	0.5 cup	99	0
skim milk	1 cup	83	0
	Total:	421	2

# Document History – Changes compared to previous final version of SAP

r		1	
	Creation of amendment 1	Addition of box plot for serum ferritin	Section 2.4.2 – Statistical hypothesis, model, and method of analysis
	Creation of amendment 1	Removal of supportive analysis	Section 2.4.4 – Supportive analysis
	Creation of amendment 1	Addition of treatment emergent definition. Addition of clear categories of ocular AESI	Section 2.5.2 - Statistical hypothesis, model, and method of analysis
	Creation of amendment 1	Following updates and clarifications added to for the of Ocular data analyses to address HA request: -	
		Clarification of definition of Ocular examinations; summary table ; additional of swimmers plot for key ocular assessment on treatment periods and post treatment periods;	
		Clarification of LogMAR conversion method and	Section 2.6.2 – Ocular examinations

detailed analysis for Visual acuity ;Addition of clear analysis of Slit lamp, summary table, shift table, listing for abnormalities, listing for MedDRA coded term.Addition of clear analysis of Fundus Oculi, Table and listing for other abnormal findings MedDRA coded term;Addition of analysis - summary table and listing for the color fundus photography with and without abnormalities, Additional listing for findings; general comments and confidence score comments.	
Creation of amendment 1Clear specification of AEs Analysis; summary tablesSection 2.6.3 Adverse Event	

		for different categories.	
		Addition of separate table of secondary safety objective on the evaluation of safety and tolerability of deferasirox FCT in subjects who interrupt to SF $\leq$ 100 µg/L and re- initiate therapy when $\geq$ 300 µg/L.	
		analysis related to COVID-19 AEs.	
	Creation of amendment 1	clear specification of AESI Analysis, summary tables.	Section 2.6.5 - Adverse Event of Special Interest (AESI)
	Creation of amendment 1	Addition of disclosure related output	Section 2.6.6 – Disclosure related outputs
	Creation of amendment 1	Addition of descriptive statistics for the lab results.; redefinition of notable range for Hemoglobin, creatinine clearance.	
		Addition of conversion factor for the lab parameter – urinary protein / creatinine ratio. Addition of summaries of	Section 2.6.7 – Laboratory data

	individual liver	
	function	
	parameters like	
	ALT, AST etc.	
Creation of	redefinition of	
amendment 1	notable range vital sign(weight)	Section 2.6.8 - Vital Signs and Weight
Creation of amendment 1	Addition of analysis related to COVID-19 AEs.	Section 4 – Change to protocol specified analyses
Creation of amendment 1	Addition of Date imputation for AE, LB, CM etc.	Section 5.1 – Imputation rules
Creation of amendment 1	Update on End of treatment for Time windows for laboratory assessment	Section 5.3.1 – Safety laboratory assessments
Creation of amendment 1	Addition of Ocular assessment	
	analysis and window period	Section 5.3.2 – Ocular assessments
Creation of amendment 1	Addition of reference	Section 6 - Reference

# List of Abbreviations

AE	Adverse event
AESI	Adverse events of special interest
ALT	Alanine aminotransferase
ALP	Alkaline Phosphatase
AST	Aspartate aminotransferase
ATC	Anatomical Therapeutic Classification
BCVA	Best Corrected Visual Acuity
CRS	Case Retrieval Sheet
CSR	Clinical Study report
ETDRS	Early Treatment Diabetic Retinopathy Study
FAS	Full Analysis Set
DAR	Dose Administration Record
DI	Dose Intensity
DRL	Drug Reference Listing
FCT	Film-Coated Tablet
ECG	Electrocardiogram
eCRF	Electronic Case Report Form
EOT	End Of Treatment
EOS	End of study
HGLT	High Level Group Term
HLT	High Level Term
IVR	Interactive Voice Response
MedDRA	Medical Dictionary for Drug Regulatory Affairs
NMQ	Novartis MedDRA Queries
PDI	Planned Dose Intensity
РТ	Preferred Term
RDI	Relative Dose Intensity
RR	Response Rate
SAP	Statistical Analysis Plan
SAE	Serious Adverse Event
SF	Serum Ferritin
SMQ	Standardized MedDRA Queries
SOC	System Organ Class
TFLs	Tables, Figures, Listings
TBL	Total Bilirubin
TTR	Time To Response
WHO	World Health Organization
	-

# 1 Introduction

This statistical analysis plan (SAP) describes all planned analyses for the clinical study report (CSR) of study CICL670F2203, a phase II, multicenter, open-label, randomized two-year study to evaluate the efficacy and safety of deferasirox film-coated tablet versus phlebotomy in subjects with Hereditary Hemochromatosis.

The content of this SAP is based on protocol CICL670F2203 version 01. All decisions regarding final analysis, as defined in the SAP document, have been made prior to database lock of the study data.

The CSR SAP is located at the following CREDI location:

/CREDI Projects/I/ICL670F/CREDI Studies/ICL670F2203/Administrative Files (study level)/RAP or RAMP Meeting – CICL670F2203\_SAP (Statistical Analysis Plan)

# 1.1 Study Design

This is a randomized, multicenter, open-label, two-year, Phase II study to evaluate the efficacy and safety of deferasirox Film-Coated Tablet (FCT) versus phlebotomy in subjects with Hereditary Hemochromatosis with iron overload.

Eligible subjects will be identified during a 4-week screening period, then randomized to either deferasirox FCT or phlebotomy beginning on Day 1 and treated for 24 months (104 weeks). A total of 150 adults were planned to be randomized in a 2:1 ratio (100 subjects to deferasirox FCT and 50 subjects to phlebotomy). The present study is being conducted to fulfill post-marketing requirements for EXJADE.

After end of treatment (EOT), there is a standard 30-day safety follow-up. If a subject discontinues from treatment in either arm and has completed at least 6 months of assessments, they will be encouraged to continue in a Post-treatment Ocular Follow-up phase and undergo ocular exams every 6 months as scheduled to receive a total of at least 5 ophthalmological examinations. End of study (EOS) occurs after the last subject has completed last visit which includes a 30-day safety follow-up. This last subject may have either completed 24 months (104 weeks) of treatment, or prematurely discontinued and completed ocular assessments. After completing the study or discontinuing from study treatment, subjects will receive standard of care.

The primary analysis will be conducted on all subjects' data after final database lock. No interim analysis is planned.

The present study is being conducted to fulfill post-marketing commitments/ requirements for EXJADE PMC 750-10, NDA 021882) and JADENU (PMR 2888-8, NDA 206910).

# **1.2 Study Objectives and Endpoints**

The study objectives as outlined in the [protocol Section 3] are as follows (Table 1-1).

Objective	Endpoint	Analysis
Primary		Refer to
Assess the response rate in the deferasirox FCT and phlebotomy treatment arms where response is defined by achieving target SF $\leq$ 100 µg/L on or before 24 months.	Proportion of Subjects achieving target $SF \le 100 \ \mu g/L$ for the first time.	Section 2.5
Key Secondary		Refer to
Characterize the ocular safety of deferasirox FCT and phlebotomy over 24 months.	Incidence of ocular AEs overall and by severity, type of AE, and relation to study treatment.	Section 2.6
Secondary		Refer to
Evaluate the safety and tolerability of deferasirox FCT and phlebotomy over 24 months.	Incidence of AEs, AEs leading to discontinuation from study, laboratory abnormalities, and deaths.	Sections 2.8
Assess the change from baseline in visual acuity, intra-ocular pressure, retina or/and optic nerve abnormalities, and lens abnormalities at months 6, 12, 18, and 24 of deferasirox FCT and phlebotomy.	Change from baseline at months 6, 12, 18 and 24 in visual acuity, tonometry, slit lamp, and fundus exams.	Section 2.8.1
Assess the safety and tolerability of deferasirox FCT in subjects who interrupt and re-initiate treatment due to SF levels $\leq 100 \ \mu g/L$ and $\geq 300 \ \mu g/L$ .	Incidence of AEs in subjects who interrupt due to reaching target SF $\leq 100 \ \mu$ g/L, then re-initiate therapy at $\geq 300 \ \mu$ g/L.	Sections 2.8
Assess the first time to response (defined as $SF \le 100 \ \mu g/L$ ) between the deferasirox and phlebotomy treatment groups.	Time to reach target $SF \le 100 \ \mu g/L$ in the deferasirox and phlebotomy arms for the first time.	Section 2.7

Table 1-1 Objectives and related endpoints

# 2 Statistical Methods

# 2.1 Data Analysis General Information

Data will be analyzed by Novartis Oncology Biostatistics and Statistical Programming personnel according to the data analysis Section 10 of the study protocol as detailed in this analysis plan.

SAS® version 9.4 (or later version if available at time of database lock) will be used to perform all data analyses and to generate tables, figures, and listings.

# Data Included in the Analysis

Data from all subjects who signed informed consent will be used in the analysis. All statistical analyses described hereafter will be performed using all data collected in the database up to the final database lock date. The final database lock date will be established after all randomized

Novartis	Confidential	Page 12 of 36
SAP Amendment 1		Study No. CICL670F2203

subjects have completed 24 months of treatment including safety follow-up if applicable, or have discontinued from the study (see Protocol Section 4.3 for more details).

#### **General Analysis Conventions**

**Pooling of centers:** Unless specified otherwise, data from all study centers will be pooled for the analysis. Due to expected small number of subjects enrolled at centers, no center effect will be assessed.

**Qualitative/categorical data** (e.g., sex, race) will be summarized by frequency counts and percentages. Percentages will be calculated using the number of subjects in the relevant treatment arm as the denominator.

**Continuous data** (e.g., age, body weight) will be summarized using appropriate descriptive statistics (i.e. mean, standard deviation, median, minimum, and maximum) by treatment arm. Lower and upper quartiles will also be presented when applicable.

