7.2.2.5 Ocular examination

Ophthalmologic examinations must be conducted approximately every 6 months for at least 5 ocular assessments at screening and Weeks 24, 52, 76, and 104 (EOT).

An exception is for patients eligible for the Post-treatment Ocular Follow-up phase and EOT occurs in the interval between the scheduled 6-month exams (the allowed assessment window is 30 days +/- of the scheduled date), an ophthalmologic exam is part of the EOT then they will continue their regular schedule of ophthalmological exams every 6 months (recorded in Post-treatment follow-up eCRFs at Weeks 52, 76 and 104 as appropriate) for a total of 6 ocular examinations. A reminder by the site at least one month prior to each upcoming ophthalmological visit should be made. To provide consistent assessments, it is recommended that ocular assessments be performed at the same site with the same equipment for each patient.

The ophthalmologic examination includes the following assessments:

- Best corrected visual acuity must be done using Early Treatment Diabetic Retinopathy Study (ETDRS)
- Slit lamp examination: any opacity graded using the Lens Opacities Classification System, version III (LOCS III)
- Intraocular pressure (IOP) measured by tonometry should be performed after the above two ocular tests
- Dilated fundus exam and color fundus photography

The dilated fundus exam must assess the vitreous, retina, macula, and optic nerve for both eyes. Wide-angle fundus photography of the retina and optic nerve is preferred; however, if unavailable, a regular camera capturing 7 standard stereoscopic fields is allowed.

Detailed instructions for the ophthalmic assessments are provided in the "Manual of Ophthalmic Procedures".

 Table 7-2
 Central imaging assessments collection plan

	00	•
Procedure	Baseline	During Treatment
Color Fundus Photography	Required	Every 6 months (Screening and weeks 24, 52, 76, and 104)

The ocular examination will be performed by a local, qualified ophthalmologist and the results will be documented on the eCRF page. The color fundus photography will not be reported locally and instead be sent to an imaging Contract Research Organization (CRO) designated by Novartis for reading.

Novartis	
Amended Protocol Version 01 (Clean)	

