# **Secondary Safety Objectives**

Secondary safety objectives include:

- Assessment of change from baseline in visual acuity, intra-ocular pressure, retina or/and optic nerve abnormalities, and lens abnormalities at months 6, 12, 18, and 24.
- Evaluation of safety and tolerability of deferasirox FCT and phlebotomy over 24 months
- Evaluation of safety and tolerability of deferasirox FCT in subjects who interrupt due to  $SF \le 100 \ \mu g/L$  and re-initiate therapy when  $\ge 300 \ \mu g/L$ .

Unless otherwise specified, the following analyses will be performed by treatment arm on the Safety Set. All data, regardless of observation period, will be listed by treatment arm. Safety assessments starting during the pre-treatment or post-treatment period will be flagged in the listings. Safety assessments starting prior to study day 1 will appear with negative study day in the listings.

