#### Fundus Oculi

For each considered evaluation type (Peripheral Retina, Macula, Optic Nerve, & Vitreous Hemorrhage) and eye side, the number & percentage of subjects with and without abnormality will be provided by timepoint, eye side and treatment arm. In addition, shift table will be generated to present the worst post-baseline changes compared to baseline by eye side and treatment arm. A listing of subjects with any abnormality will be provided. Subjects with abnormalities recorded in free text of "Other Findings (Abnormalities)" section of the "Dilated Fundus Examination" CRF will be coded using MedDRA (version 26.0) and these coded ocular terms will be summarized by timepoints using frequency counts and percentages. A listing for the MedDRA coded ocular terms will also be presented.

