#### **Color Fundus Photography**

The Color Fundus Photography Assessment will be conducted by a central vendor though photographs. For each considered evaluation type and eye side, the number & percentage of subjects with and without abnormality will be provided by timepoint and treatment arm. A listing of subjects will be provided; additionally, listings for the findings, general comments and confidence score comments will be presented.

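### By-visit fundus, fundus-photography and coded eye-finding percentages are divided by the whole arm, so they shrink as exams go missing and are not on the baseline column's scale

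*SAP*

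**What the plan says.** SAP 2.1, under General Analysis Conventions, fixes the denominator for all categorical data: "Percentages will be calculated using the number of subjects in the relevant treatment arm as the denominator". It makes no exception for data tabulated by visit. The only let-out in that section concerns the pooling of centres.

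SAP 2.6.2 then specifies the ocular tables, which are run by arm on the Safety Set:

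- **Fundus oculi.** By visit, "the number & percentage of subjects with and without abnormality will be provided by timepoint, eye side and treatment arm". The only shift table collapses time: "shift table will be generated to present the worst post-baseline changes compared to baseline by eye side and treatment arm". Findings entered as free text are coded, and "these coded ocular terms will be summarized by timepoints using frequency counts and percentages".
- **Colour fundus photography.** By visit, "the number & percentage of subjects with and without abnormality will be provided by timepoint and treatment arm". The rest is listings: "additionally, listings for the findings, general comments and confidence score comments will be presented". Protocol 7.2.2.5 adds that there is no local reading to fall back on: "The color fundus photography will not be reported locally and instead be sent to an imaging Contract Research Organization".
- **Slit lamp.** It has similar by-visit counts and coded-term tables, but also shift tables at each visit.

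None of these names another denominator or a row for subjects not examined. A missing category is specified for demographics (SAP, Basic Demographic Data) but not here. SAP 2.6.2 does plan a separate table of completed ocular assessments by eye, type of evaluation, visit and arm.

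**The concern.** The secondary safety objective covers change from baseline in "retina or/and optic nerve abnormalities, and lens abnormalities at months 6, 12, 18, and 24", in a trial run partly to confirm two-year ocular safety for a regulator. A reader will compare the baseline column with the later ones. Under the SAP rule, a subject not examined at a visit stays in the denominator but appears in neither the *with* nor the *without* row. The printed percentage therefore mixes the finding rate with exam completion, and it can fall while the rate among those examined is flat or rising.

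Exposure differs by examination. Visual acuity, intraocular pressure, slit lamp and LOCS III also have shift tables at each visit, which cross-classify the visit against baseline. Fundus oculi has only the worst-post-baseline shift table and photography has none. For retina and optic nerve, the affected tables are thus the only specified summaries of rates by month.

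**Working it through.** **Inputs**

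- Planned arm size: 100 deferasirox and 50 phlebotomy (SAP 1.1). The deferasirox arm is used below.
- Baseline completeness: taken as 1.00, because the eye exam is scheduled at screening for both arms (Protocol 7.1.2, Table 7-1) and required before deferasirox (Protocol Table 6-2). An assumed 0.90 is also shown.
- Fraction examined late in the study, *f*:
  - 0.60, the planning minimum of 60 out of 100 deferasirox patients (SAP 3).
  - 0.76, which is 1 − 0.24, using the Month 6 dropout of an earlier study of the other formulation (SAP 3). It is a marker on the range, not an estimate for Week 104, and the plan expects better compliance.
  - 0.90, assumed.
- Finding rates of 20%, 30% and 5% are assumed for illustration.

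**The plan's retention figure.** It states no percentage for ocular findings, so the figure to reproduce is the minimum of 60. After 24% dropout, 100 × 0.76 = 76 remain at Month 6. A further 12% leaves 76 × 0.88 = 66.9 at Month 12 if it applies to those remaining, or 76 − 12 = 64 if it applies to the original 100. Ending with 60 allows a further loss of 1 − 60/66.9 = 10.3%, or 1 − 60/64 = 6.3%. Both fit the stated assumption that dropout declines, so 60 is coherent as a planning minimum.

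**Formula.** Printed % = (examined with finding) / N = (rate among examined) × *f*.

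The printed figure rises from baseline only if the examined rate rises by more than the break-even factor, baseline completeness / *f*.

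| *f* | Flat 20%: *with* / *without* rows | True rise to 30% prints as | Break-even, baseline 1.00 | Break-even, baseline 0.90 |
|---|---|---|---|---|
| 0.60 | 12.0% / 48.0% | 18.0% | 1.67 | 1.50 |
| 0.76 | 15.2% / 60.8% | 22.8% | 1.32 | 1.18 |
| 0.90 | 18.0% / 72.0% | 27.0% | 1.11 | 1.00 |

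The baseline column prints 20% if complete and 0.90 × 20% = 18% if 90% complete. A rise from 20% to 30% therefore prints as a fall only at *f* = 0.60 with a complete baseline. With a 90% complete baseline and *f* = 0.60 it prints as 18% both times.

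**Can a reader undo it?** Where every examined subject falls in the *with* or the *without* row, yes: 12/(12 + 48) = 20%. The coded-term tables have no *without* row. Five subjects with a term among 100 examined at baseline, and five among 60 examined at Week 104, both print as 5/100 = 5%. The examined rates are 5.0% and 5/60 = 8.3%, a ratio of 1.67. Only the separate completion table reveals this.

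**Which visits.** The Week 24 window runs from day 2 to day 259 (SAP Table 5-4), so it can capture early end-of-treatment exams. The effect falls mainly on later visits.

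**The case against.** The strongest reply is that nothing is lost. The completion table gives the missing denominator at the right level of detail, and the fundus and photography tables let the reader add two counts. That is true, and it keeps the point minor. It does not help someone reading a coded-term table alone, and a safety table should not need a second table to be read correctly.

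By-visit denominators are often set in table shells, which are not among the documents. The shells may already use the number examined. If so, they conflict with SAP 2.1 as written, and a sentence should reconcile them.

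Missing exams may be fewer than illustrated. Protocol 7.1.5 does not treat patients who stop treatment as withdrawn, says they should return for the ocular assessments, and asks for every effort to reach those who do not. The windows run without gaps from day 2 to day 819 and include post-treatment exams. This lessens the effect without removing it. Post-treatment ocular follow-up is only encouraged, and only after six months of assessments (Protocol 4.1.1). SAP 4 also records COVID-19 delays.

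A retinal signal could surface elsewhere. Retinal and optic-nerve adverse events are analysed under the key secondary objective, and swimmer plots are planned for ocular assessments that are not all named. Both are safeguards, but neither gives a rate by month.

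The contrast with the other exams should not be overstated. Their shift tables help by cross-classifying against baseline. The SAP exempts no percentages in them from the full-arm rule.

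Finally, examined-only percentages still compare partly different people across visits and can be biased if missing exams are informative. That stands, and is why the missing row belongs beside them.

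**Conclusion.** The concern holds as a minor point. The SAP states a full-arm denominator and nothing in SAP 2.6.2 overrides it, so later by-visit percentages in these tables are scaled down by the fraction examined. At examined fractions of 0.60 to 0.90, an unchanged 20% prints as 12% to 18%. The figures are illustrations, not forecasts: actual completion is not given, 0.60 is a planning minimum, and the finding rates are assumed. The size and direction of any between-arm distortion are unknown, because no document gives completion for phlebotomy. The primary response rate and the key secondary ocular adverse event incidence do not depend on this rule for by-visit exams, and no hypothesis is tested. Confidence is medium, chiefly because the shells were not available.

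**What to change.** Add one sentence to SAP 2.6.2: percentages in by-visit ocular tables use, as denominator, the subjects with a non-missing assessment of that evaluation type and eye at that visit. They are shown as n/m (%) with a row for missing assessments, and the rule also covers the MedDRA-coded and free-text finding tables. Keep the full-arm denominator for response rate, adverse event incidence and disposition. If the shells already do this, say so in SAP 2.6.2, since SAP 2.1 says otherwise.

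The cost is that sentence and a change to the shells, with no new data and no change to any endpoint. Printed late-visit percentages would be larger by a factor of 1/0.90 = 1.11 to 1/0.60 = 1.67 over the range considered. The change does not cure informative missingness.
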